Pharmacological intervention: Following completion of Visit 4, subjects will be randomized to receive, in a double-blind fashion, placebo (maltodextrin, 6 g three times a day), the synbiotic [5 g of oligofrucose + 1 g Bifidobacterium longum (4x10^10 CFU/g) three times a day], or sevelamer (1.6 g sevelamer + 4.4 g maltodextrin three times a day), for 4 weeks, and discharged home. Sevelamer is obtained from Amgen (Renvela, Cambridge, MA), oligofructose from Orafti (Tienen, Belgium), Bifidobacterium from Danisco (Copenhagen, Denmark) and maltodextrin from American International Foods (Grand Rapids, MI). Randomization and drug preparation/dispensing is performed by the Research Pharmacist of the BRU. For each dose the powder will be included in identical packets. The subjects from the 3 groups (placebo, synbiotic, sevelamer) will ingest the powder contained in one packet with water 3 times /day. Medication willb e given for up to 32 days. Appointment time frame for study medication will be 26-32 days to allow for patient scheduling and weekends.

Before discharge, subjects are given printed instructions and information about potential side effects.

IRB #	HSC20130458H

Visit 5: Approximately on day 24 of treatment, subjects will come to the BRU at 7 AM in the fasting state to undergo stool sample collection, and an 5h intestinal permeability (lactulose/mannitol) testing. Labs for analyses as in Visit 3 are repeated. Note: Scheduling window varies – ideally to occur within 1 week prior to Visit 6 clamp and total days of study medication.

Visit 6: Approximately on day 28 (between days 26 and 32) of treatment, subjects will come to the BRU at 7 AM to undergo DEXA, insulin clamp, indirect calorimetry, and biopsies of the muscle (2) as described above for Visit 4. A pregnancy test is performed if applicable. Labs as in Visit 3 are repeated (see Analyses below).

Analyses. Plasma LPS, LBP, soluble CD14, IL-6, TNF α and phosphate will be measured before, during, and afer treatment (Visits 3, 4, 5, and 6). Assays of TLR4 and insulin signaling in muscle are performed as described for Aim 1. Stool samples (Visits 3 and 5) will be collected before and during treatments. This will allow us to evaluate differences in microbiome composition between lean, obese, and T2DM subjects at baseline, and establish the relationship between treatment-induced changes in specific bacteria composition/distribution with changes in inflammation and insulin action.

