Analyses. Plasma LPS, LBP, soluble CD14, IL-6, TNF α and phosphate will be measured before, during, and after treatment (Visits 3, 4, 5 and 6). Assays of TLR4 and insulin signaling in muscle are performed as described for Aim 1. Stool samples will be collected before and during treatments. This will allow us to evaluate differences in microbiome composition between lean, obese, and T2DM subjects at baseline, and establish the relationship between treatment-induced changes in specific bacteria composition/distribution with changes in inflammation and insulin action.

4. Study Population(s).

You will be drawing subjects from one or more populations. In medical research, for example, a population can be individuals with type 2 diabetes controlled with diet, or a population of healthy individuals. In social behavioral research, a population can be individuals attending an education program, etc.

4.a. How many different populations are you enrolling in this study?	3
4.b. For each different population, provide a short descriptive label : (e.g., normal-healthy, diabetics, parents, children, etc.) Copy and paste additional labels as needed →	 Lean nondiabetic Obese nondiabetic Obese type 2 diabetic

4.c.	4.c. For each specific population identified in 4b, provide the following information in the table provided below.				
	(For studies with more than one population, copy all of table 4.c. and paste to insert additional tables.)				
Population # 1 Population Descriptive Label: Lean nondiabetic		Population Descriptive Label: Lean nondiabetic			
(1) Identify the criteria for inclusion:		e criteria for inclusion :			

#	HSC20130458H		
1) Bo 2) All 3) Pro 4) Po 5) HC 6) Sta 7) Tw 8) BM	th genders between ages 18-65 years, without family history of diabetes. races and ethnic groups. emenopausal women in the follicular phase, non-lactating, and with a negative pregnancy test. stmenopausal women on stable dose of or not exposed to hormone replacement for \geq 6 months. CT \geq 34%, serum creatinine \leq 1.4 mg/dl, electrolytes, urinalysis, and coagulation tests. LFTs up to 2X. able body weight (±2%) for \geq 3 months. γ or less sessions of strenuous exercise/wk for last 6 months η <26 kg/m2 rmal glucose tolerance based on ADA criteria		
(2)	Identify the criteria for exclusion :		

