2) Fa 3) Cu past 3 recep 4) His 5) No 6) Cu held 1 7) Us 8) His on th 9) Po 10) A	 Presence of impaired glucose tolerance or type 2 diabetes based on ADA criteria Family history of diabetes (parents, siblings, children) Current treatment with drugs known to affect glucose and lipid homeostasis. If the subject has been on a stable dose for the past 3 months, the following agents will be permitted: calcium channel blockers, beta-blockers, ACE inhibitors, angiotensin receptor blockers, and statins. History of allergy to sevelamer. Non-steroidal anti-inflammatory drugs or systemic steroid use for more than a week within 3 months. Current treatment with anticoagulants (warfarin). Aspirin (up to 325 mg) and clopidogrel will be permitted if these can be held for seven days prior to the biopsy in accordance with the primary physician. Use of agents that affect gut flora (e.g. antibiotics, colestyramine, lactulose, PEG) within 3 months. History of heart disease (New York Heart Classification greater than grade II; more than non-specific ST-T wave changes on the ECG), peripheral vascular disease, pulmonary disease, smokers. Poorly controlled blood pressure (systolic BP>170, diastolic BP>95 mmHg). Active inflammatory, autoimmune, hepatic, gastrointestinal, malignant, and psychiatric disease. 		
,	istory of gastrointestinal surgery or gastrointestinal obstruction within two years. Recruitment Process – identifying potential subjects		
(3)	Describe plans about how the population will be identified for the purpose of recruiting. (e.g., database search, personal contacts, referrals, patients under the care of the research team, etc.) (Consider Form J, HIPAA Waiver to access PHI for identification of potential subjects)		
All su	bjects will be recruited through advertisement in local newspapers, radio and the web.		

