	Subjects will consent after the purpose, nature, and potential of the risks of the study are explained during a pre-recruitment interview or immediately before initiating Visit 1. Subjects may also take the consent to home, and sign the consent during a follow-up interview or on Visit 1 (before initiating the procedures).				
	(9) Describe measures taken to minimize the possibility of coercion or undue influence during consent.				
	After explaining the study, subjects will be allowed to read the consent freely and with sufficient time. Subjects will not be pressured in any way to enter the study. We will explain that the study is voluntary and that if they decide not to participat exit the study) they (and their family members) will not be punished in any way, and this will not affect their eligibility to enter turn studies or to seek medical treatment at the Audie L. Murphy VAMC or UTHSCSA.				
	Will subjects from this population be assigned to different research groups? (e.g., treatment and control group)				
	(10)	Yes No			
	If yes, list the groups by inserting a short descriptive title for each group. E.g., experimental group A, B, etc., control group, etc. - these labels are needed for the Risk: Benefit Analysis section Control: This group will receive placebo Experimental/Synbiotic: This group will receive a symbiotic (Bifidobacterium longum plus oligofructose) Experimental/Sevelamer: This group will receive sevelamer				
4.c.	For ea	ach specific population identified in 4b , provide the following information in the table provided below.			
		(For studies with more than one population, copy all of table 4.c. and paste to insert additional tables.)			
Рор	ulatior	#2 Population Descriptive Label: Obese nondiabetic			
	(1)	Identify the criteria for inclusion :			
	 Both genders between ages 18-65 years old, with or without family history of diabetes All races and ethnic groups. BMI 30-37 kg/m2. Stable body weight (±2%) for ≥ 3 months. Normal glucose tolerance based on ADA criteria. Two or less sessions of strenuous exercise/wk for last 6 months Premenopausal women in the follicular phase, non-lactating, and with a negative pregnancy test. Postmenopausal womer on stable dose of or not exposed to hormone replacement for ≥6 months. HCT≥ 34%, serum creatinine ≤ 1.4 mg/dl, electrolytes, urinalysis, and coagulation tests. LFTs up to 2X. 				
	(2)	Identify the criteria for exclusion :			

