	After explaining the study, subjects will be allowed to read the consent freely and with sufficient time. Subjects will not be pressured in any way to enter the study. We will explain that the study is voluntary and that if they decide not to participate exit the study) they (and their family members) will not be punished in any way, and this will not affect their eligibility to enter future studies or to seek medical treatment at the Audie L. Murphy VAMC or UTHSCSA.					
	(10)	Will subje	cts from this population be assigned to different research groups? (e.g., treatment and control group)			
	(10)	Ye:	s 🔲 No			
		-	oups by inserting a short descriptive title for each group.			
	-	-	ntal group A, B, etc., control group, etc these labels are needed for the Risk: Benefit Analysis section up will receive placebo			
		•	nbiotic: This group will receive a synbiotic (Bifidobacterium longum plus oligofructose)			
			velamer: This group will receive sevelamer			
4.0	F an a	a a la cara a ifi a				
4.C.	For ea	ach specific	population identified in 4b , provide the following information in the table provided below. (For studies with more than one population, copy all of table 4.c. and paste to insert additional tables.)			
Pop	ulation	# 3	Population Descriptive Label: Obese – type 2 diabetic			
	(1)		e criteria for inclusion :			
		•	between ages 18-65 years old, with or without family history of diabetes.			
	 2) All races and ethnic groups. 3) BMI 30-37 kg/m2. Stable body weight (±2%) for ≥ 3 months. 4) T2DM with HbA1C ≤ 8.5% 5) Two or less sessions of strenuous exercise/wk for last 6 months 6) Premenopausal women in the follicular phase, non-lactating, and with a negative pregnancy test. Postmenopausal women on stable dose of or not exposed to hormone replacement for ≥6 months. 7) HCT≥ 34%, serum creatinine ≤ 1.4 mg/dl, with normal electrolytes, urinalysis, and coagulation tests. LFTs up to 2X. 8) Based on OGTT (Visit 2), ADA criteria of Type 2 diabetes 					
	(2)	•	e criteria for exclusion :			

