Purpose/Objectives: Insulin resistance in peripheral tissues (i.e. skeletal muscle) is one of the earliest and most significant abnormalities in the pathogenesis of type 2 diabetes (T2DM). However, the molecular basis for the insulin resistance of T2DM is not fully understood. The human gut hosts an enormous number and variety of microorganisms, including at least 1014 bacteria. An increasing number of animal studies suggest that this microbial "organ", also known as the microbiome, is a causative factor in the insulin resistance of obesity and T2DM, and may represent an entirely new therapeutic target against these conditions. These studies suggest that high fat ingestion, obesity, and T2DM, favor a microbiome profile which enhances production and gastrointestinal permeability of lipopolysaccharide (i.e. metabolic endotoxemia). Lipopolysaccharide (LPS or endotoxin) is a component of the outer membrane of gram negative bacteria cell walls which induces an inflammatory response by activating the cell surface receptor toll-like receptor-4 (TLR4). Despite accumulating evidence from animal studies suggesting that intestinal microbiome and metabolic endotoxemia on human metabolic disease remains unknown. Thus, the goal of this study is to determine the role that intestinal microbiota and metabolic endotoxemia play in the pathogenesis of insulin resistance and T2DM in humans.

Research Design/Plan: We will study three groups of subjects: 1) 36 healthy, 18-65 yrs old, normal-glucose tolerant subjects, without a family history of T2DM, and body mass index (BMI) of \leq 26 kg/m²; 2) 36 obese, 18-65 yrs old, normal-glucose tolerant subjects, with or without a family history of T2DM, and body mass index (BMI) of 30-37 kg/m²; 3) 36 obese, 18-65 yrs old, T2DM with or without a family history of T2DM, HbA1C \leq 8.5%, and body mass index (BMI) of 30-37 kg/m². All subjects will undergo pharmacological intervention. All subjects will be studied at the Bartter Research Unit (BRU) at the Audie L. Murphy VA Medical Center, as follows;

Visit 1: Screening tests including a complete history and physical examination/assessment, ECG, blood chemistry, blood cell count, HbA1c, PT, PTT, lipid profile, and UA.

Visit 2: OGTT.

Visit 3: Stool sample collection, plasma LPS measurement, and an 8 h intestinal permeability (lactulose/mannitol) testing.

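### Family history of diabetes is barred in lean subjects but allowed in obese subjects, so the unadjusted lean–obese baseline contrast mixes obesity with familial diabetes risk

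*Combined protocol and SAP*

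**What the plan says.** Section 4.c, Population 1 (lean nondiabetic), requires subjects "without family history of diabetes". Its exclusion list repeats the bar and defines the relatives: "Family history of diabetes (parents, siblings, children".

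Section 4.c, Population 2 (obese nondiabetic), admits subjects "with or without family history of diabetes". Population 3 (obese type 2 diabetic) has the same permission. The Abstract repeats the split: its lean group is without a family history, and its obese group is "36 obese, 18-65 yrs old, normal-glucose tolerant subjects, with or without a family history of T2DM". The difference is consistent across the document, so it is a design choice and not a slip.

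Sections 3 and 6.a (Analyses) say the stool samples will be used to "evaluate differences in microbiome composition between lean, obese, and T2DM subjects at baseline". Section 6.a (Statistical analysis) compares means between all groups by repeated-measures ANOVA, compares correlation coefficients between groups, and tabulates power for lean versus obese and lean versus T2DM. It names no family-history term, stratum, restriction or sensitivity analysis. Multiple regression is planned for the LPS relationships, with no covariates listed.

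**The concern.** The populations are not randomized against each other, so the meaning of a baseline difference depends on how each was selected. The lean and obese nondiabetic groups differ in BMI by intent. They also differ in family history by rule: none in the lean group, any proportion in the obese group. Both must have normal glucose tolerance, which limits overt dysglycemia but does not equalize familial risk.

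If family history is related to LPS, TLR4 signaling, insulin action or the microbiome, part of a lean–obese difference in these measures belongs to it. The documents do not say that it is so related, but excluding affected relatives from the lean group treats it as potentially relevant. At stake is the interpretation of the baseline findings, which bear on the study's stated question about the pathogenesis of insulin resistance.

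Lean versus T2DM has the same asymmetry, but there inherited risk can be regarded as part of the disease being contrasted. The problem is clearest for lean versus obese nondiabetic.

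**Working it through.** The plan gives no figure for this point, so there is none to reproduce. The check has three parts.

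**1. How large could the bias be?**

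Inputs from the documents: 36 subjects per population (Abstract); 12 per group and two-sided α = 0.05 (section 6.a). Assumed inputs, not in the documents: share of obese subjects with a family history, p = 0.30 to 0.70; effect of family history on a baseline outcome, f = 0.3 to 0.5 SD.

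With no family history in the lean group, bias = p × f.
- Low: 0.30 × 0.3 = 0.09 SD
- High: 0.70 × 0.5 = 0.35 SD

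Suppose obesity has no effect. A two-sample t test with n per group then has noncentrality bias × √(n/2), and the noncentral t distribution gives these rejection probabilities:

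| n per group | Bias 0.09 SD | Bias 0.35 SD |
|---|---|---|
| 36 (whole population) | noncentrality 0.38, rejects 6.6% | noncentrality 1.48, rejects 31.0% |
| 12 (planning size) | noncentrality 0.22, rejects 5.5% | noncentrality 0.86, rejects 13.0% |

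The nominal rate is 5%. Baseline precedes treatment, so all 36 subjects in a population can enter the contrast; the second row shows the result at the size used for the power calculation. Wider assumptions widen the range: p = 0.25 to 0.75 with f = 0.2 to 0.8 SD gives a bias of 0.05 to 0.60 SD.

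**2. Can the analysis separate the two factors?**

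The lean and obese nondiabetic data form three cells: lean without family history, obese without, and obese with. Fit

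mean = a + b × obese + c × family history.

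Three parameters describe three cell means, so the model is saturated:
- a = mean(lean)
- b = mean(obese without) − mean(lean)
- c = mean(obese with) − mean(obese without)

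The obesity coefficient b is exactly the contrast restricted to obese subjects without a family history. A fit to simulated data confirmed that the two estimates are identical. What cannot be estimated is the effect of obesity among people with a family history, because no lean subject has one. The exact equality also requires that the model holds only these two populations and no further covariates.

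**3. What does the restricted contrast cost?**

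At p = 0.70, 36 × 0.30 = 10.8, so about 11 obese subjects remain. At p = 0.30, 36 × 0.70 = 25.2, so about 25 remain. The standard error in SD units is √(1/36 + 1/m), where m is the number of obese subjects used.

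| Obese subjects in the contrast | Standard error | Difference detectable with 80% power |
|---|---|---|
| 36 (all) | 0.236 SD | 0.67 SD |
| 25 | 0.260 SD | 0.74 SD |
| 11 | 0.345 SD | 0.99 SD |

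The comparison of obese subjects with and without a family history has about 13% power for 0.3 SD. For 0.5 SD it has about 27% with an 11/25 split and 31% with an even split.

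**The case against.** Five points can be made for the plan.

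*The lean group is a deliberate low-risk reference.* The Aim calls the other groups insulin resistant, and nowhere do the documents say that baseline differences will be credited to obesity independently of inherited risk. Clean controls are legitimate, and the rationale may lie in the grant application, to which the Background section defers. This stands. It supports a comparison of lean subjects without a family history against obese subjects, but it does not license shortening the label to lean versus obese.

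*The Aim is carried by randomized comparisons.* This stands fully. A reader might infer that the treatment comparisons are confounded too. They are not: family history is balanced in expectation between arms within a population.

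*Adjustment works.* A reader might infer that, with no family history among lean subjects, no model can separate the two factors. Part 2 of the working shows otherwise. The shortfall is that the plan specifies no such term or restriction.

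*The bias may be small beside the expected differences.* The lean–obese rows of the power table state 0.99, 0.91 and 0.99 at 12 per group. With an unpaired t test, power of 0.91 implies about 1.41 SD and power of 0.99 about 1.8 SD, so a bias of 0.35 SD is about a quarter of the smaller difference (0.35/1.41 = 0.25). For outcomes with differences that large, family history would inflate the estimate and not create the finding. Which outcomes those rows cover cannot be read in the text available to me, and the family-history criteria of the study behind them are not given.

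*Family history may not be on file for obese subjects.* The visit descriptions mention only a medical history. This stands, and it needs confirming.

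**Conclusion.** The concern holds for the non-randomized baseline contrast between lean and obese nondiabetic subjects. As planned, that contrast mixes obesity with familial diabetes risk, and nothing in the stated analysis accounts for it.

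The size cannot be determined from the documents. The range of 0.09–0.35 SD, and the corresponding 6.6–31% rejection at 36 versus 36, rest entirely on the assumed share and effect and on a true obesity effect of zero. They show what is possible and do not estimate what this study will find.

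This is an inexpensive improvement to interpretation. It gives no reason to change enrollment and no ground to doubt the treatment comparisons.

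**What to change.** 1. Confirm that family history of diabetes in parents, siblings and children is recorded at Visit 1 in all three populations.
2. In section 6.a, pre-specify a supporting lean–obese baseline contrast restricted to obese subjects without a family history, beside the all-obese contrast. Equivalently, add a family-history term to the lean–obese model, which gives the same point estimate.
3. Word the all-obese result as lean without family history versus obese.
4. Report the difference between obese subjects with and without a family history descriptively, with a confidence interval. Its low power means that a nonsignificant result would not show family history to be harmless.

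The cost is a few lines of analysis text and one item at screening. Eligibility, visits and treatment do not change. The restricted contrast is less precise, as part 3 of the working shows, so it should support the all-obese contrast and not replace it.

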You may reference sponsor's full protocol or grant application (page number and section) or if none, ensure background includes references.

a. Background

Refer to pages 1-3 of grant application.

b. Current practice

Three groups of subjects will be enrolled into this study: lean, obese nondiabetic and obese type 2 diabetic.

- The current practice for type 2 diabetic subjects is the following:
 - Lifestyle modification with dietary counseling.
 - If glycemic control is poor after 6-10 weeks, oral agents are initiated. Metformin is considered the first line agent. If control is poor with metformin, a second line agent (sulfonylurea, glitazone, DPP IV inhibitor, or GLP-1 agonist is indicated).

3. Study Design.

Describe the study design (e.g., single/double blind, parallel, crossover, etc.) Consider inserting a scheme to visually present the study design.

Visit 1: Subjects will undergo a medical history, physical examination, and screening blood tests.

Visit 2: Within 3-14 days eligible subjects will return for OGTT.

Visit 3: Within 3-21 days subjects undergo blood (LPS) and stool collection and an intestinal permeability test.

Visit 4: Within 7-21 days from Visit 3, subjects will return to undergo a whole body DEXA, indirect calorimetry and an insulin clamp. Muscle biopsies will be performed before (-30 min) and at the end (+180 min) of the clamp. Following completion of these studies, subjects will be randomized to receive in a double-blind fashion, placebo (maltodextrin, 6 g three times a day), the synbiotic [5 g of oligofrucose + 1 g Bifidobacterium longum (4x10^10 CFU/g) three times a day], or sevelamer (1.6 g sevelamer + 4.4 g maltodextrin three times a day), for 4 weeks, and discharged to home. While at home, subjects will maintain their habitual (isocaloric) diet and physical activity level.

Visit 5: Approximately on day 24of treatment blood (LPS) and stool are collected and an intestinal permeability test is done. Note: Scheduling window varies – ideally to occur within 1 week prior to Visit 6 clamp and total days of study medication.

Visit 6: Approximately on day 28 (between days 26 to 32), subjects undergo a second DEXA, indirect calorimetry, and insulin clamp with muscle biopsies.

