	 Current treatment with drugs known to affect glucose and lipid homeostasis (sulfonylureas only are permitted). If the subject has been on a stable dose for the past 3 months, the following agents will be permitted: calcium channel blockers, betablockers, ACE inhibitors, angiotensin receptor blockers, and statins. History of allergy to sevelamer. BMI <30 or >37 kg/m2 Non-steroidal anti-inflammatory drugs or systemic steroid use for more than a week within 3 months. Current treatment with anticoagulants (warfarin). Aspirin (up to 325 mg) and clopidogrel will be permitted if these can be held for seven days prior to the biopsy in accordance with the primary physician. Use of agents that affect gut flora (e.g. antibiotics, colestyramine, lactulose, PEG) within 3 months. History of heart disease (New York Heart Classification greater than grade II; more than non-specific ST-T wave changes on the ECG), peripheral vascular disease, pulmonary disease, smokers. Poorly controlled blood pressure (systolic BP>170, diastolic BP>95 mmHg). 					
	9) Act	tive inflamn	natory, autoimmune, hepatic, gastrointestinal, malignant, and psychiatric disease.			
	10) H		strointestinal surgery or gastrointestinal obstruction within two years.			
	(3)	Describe	ent Process – identifying potential subjects plans about how the population will be identified for the purpose of recruiting. (e.g., database search, contacts, referrals, patients under the care of the research team, etc.)			
		-	Form J. HIPAA Waiver to access PHI for identification of potential subjects)			

FO	RM	С

Subjects	will	be	re
	Subjects	Subjects will	Subjects will be

HSC20130458H

IRB #

Г

Clinic or the	ects will be recruited through advertisement in local in local newspapers and the web, and through the General Medicine is of the University Center for Community Health and the Audie L. Murphy VA Hospital. Patients who present to the clinic e VA will have their chart reviewed to determine if the hey meet inclusion criteria. A HIPAA Waiver and a Waiver of ent will be requested for this activity.					
	If recruiting from more than one institution and the identification process differ - clearly describe differences here.					
	New participants will first contact the researchers. The research team will then make an appointment to explain the study to the participant					

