Choose one of the choices below:					
		There is no expected direct benefit for those participating. (go to $c(1)$ and $c(2)$ below)			
There is an expected direct benefit for those participating. Provide justification why the delay is acceptable below , then (go to c(1) and c(2)below)					
Insert the reason a delay is acceptable here					
		e recruiting non-English speaking subjects, Describe the process for obtaining informed consent from bjects in their respective language (or the legally authorized representative's respective language).			
Describe here					
		to ensure that individuals are appropriately informed about the study when English is their second-language n for evaluating the level of English comprehension, and the threshold for providing a translation, or explain			

6. Research Plan / Description of the Research Methods:

6.a. Provide a **comprehensive narrative** describing the **research methods**.

Provide the order in which tests/procedures will be performed,

the setting for these events and a description of the methods used to protect privacy during the study.

Provide the **plan for data analysis** (include as applicable the **sample size calculation**)

Visit 1: Subjects will come to the BRU at 7 AM for a medical history, physical examination (including anthropometric measurements), screening tests (CBC, chemistry, lipid profile, HbA1c, PT, PTT, UA, pregnancy test if applicable), and ECG.

Visit 2: Within 3-14 days from Visit 1, eligible subjects will return at 7 AM after an overnight fast for an oral glucose tolerance test (OGTT).

Visit 3: Within 3-21 days from Visit 2, subjects will come to the BRU at 7 AM in the fasting state to undergo stool sample collection, plasma LPS, LBP measurement, inflammatory markers and phosphate (see Analyses page 11), and an 5h intestinal permeability (lactulose/mannitol) test. Serum phosphorus also will be measured.

Visit 4: Within 7-21 days from Visit 3, subjects will undergo whole body DEXA, a euglycemic hyperinsulinemic clamp and indirect calorimetry as described (44, 45). A pregnancy test is performed if applicable. DEXA is performed to examine the effect of the interventions on body composition. At time -30 min a biopsy of the vastus lateralis muscle will be performed. At time 0 min, insulin will be infused at 60 mU/m2.min for 180 min. A 2nd biopsy is performed on the contralateral leg at 180 min. Labs for analyses as in Visit 3 are repeated.

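### The T2DM criteria put no stability or look-back condition on antidiabetic drugs: this adds noise to the randomised contrast and can bias the non-randomised T2DM analyses

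*Combined protocol and SAP*

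**What the plan says.** All references are to the combined protocol and SAP.

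- **Section 4.c, Population 3, exclusion criteria.** The first item is "Current treatment with drugs known to affect glucose and lipid homeostasis (sulfonylureas only are permitted". Its next sentence begins "If the subject has been on a stable dose for the past 3 months, the following agents will be permitted: calcium channel blockers" and goes on to beta-blockers, ACE inhibitors, angiotensin receptor blockers and statins. Sulfonylureas are not on that list.
- **Same list, look-backs.** Two other items reach back in time: "Non-steroidal anti-inflammatory drugs or systemic steroid use for more than a week within 3 months" and "Use of agents that affect gut flora (e.g. antibiotics, colestyramine, lactulose, PEG) within 3 months".
- **Section 4.c, Population 3, inclusion criteria.** "Stable body weight (±2%) for ≥ 3 months" is a stability condition on weight. "T2DM with HbA1C ≤ 8.5"% limits the level of glycaemia, not its stability.
- **Section 2.b, Current practice.** "Metformin is considered the first line agent"; several second-line classes follow, sulfonylureas among them.
- **Section 3, Study Design.** Between the clamps, habitual diet and activity are to be kept. Background drugs are not mentioned.
- **Section 6.a, Statistical analysis.** Repeated-measures ANOVA, within-group Pearson correlations and multiple regression are planned. No background-drug covariate is named.

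**The concern.** The list guards against carry-over and dose drift for several drug classes, but not for the class closest to the clamp outcome. As written, a subject who stopped an antidiabetic agent, or started or changed a sulfonylurea, days before Visit 1 can enter. If that change is still working through, it is part of the baseline measurement and of the change from Visit 4 to Visit 6.

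What is at stake differs by analysis.

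- **Baseline lean/obese/T2DM contrasts.** These are not randomised, and antidiabetic exposure is essentially confined to the T2DM group. A recent change in it can be read as an effect of disease.
- **Within-group correlations in T2DM.** A recent change could move LPS, signalling and insulin sensitivity together or separately, creating or masking an association.
- **Within-arm pre/post change.** Drift in one direction does not cancel. The sevelamer rows of the power table are themselves pre/post comparisons.
- **Randomised arm-versus-placebo contrast.** Drift is balanced in expectation, so the cost is precision.

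**Working it through.** **1. Timing.** Section 6.a gives the windows. Visit 1 to Visit 2 is 3-14 days ("Within 3-14 days from Visit 1, eligible subjects will return at 7 AM"), Visit 2 to Visit 3 is 3-21 days, and Visit 3 to Visit 4 is 7-21 days. Visit 6 falls on treatment days 26-32.

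- Visit 1 to baseline clamp: minimum 3 + 3 + 7 = 13 days; maximum 14 + 21 + 21 = 56 days.
- Visit 1 to follow-up clamp: minimum 13 + 26 = 39 days; maximum 56 + 32 = 88 days.

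For a change made just before Visit 1, both clamps therefore fall within about three months, the span the list uses for other agents.

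**2. Group sizes.** The plan's inflation reproduces: 12 / (1 − 0.20) = 15 per group. The Abstract gives 36 per population; with three arms and equal allocation (the ratio is not stated), 36 / 3 = 12 per arm. The point does not depend on which of these figures stands.

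**3. Size, under assumptions.** The documents give neither the share of T2DM subjects affected (f) nor the effect on the clamp measure in SD units (k). I take f = 0.10-0.50 and k = 0.25-1.0. For scale I use the second row of the power table, T2DM 4.2 ± 1.7 and obese 8.1 ± 2.4. Its label is lost, and I assume it is insulin sensitivity. The obese-T2DM difference is 8.1 − 4.2 = 3.9. With 12 per arm, a two-sided t-test at 0.05 has 80% power for d = 1.20, a difference of 1.20 × 1.7 = 2.04.

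- Mean shift in T2DM = f × k × 1.7.
- SD inflation = √(1 + f(1 − f)k²), then noncentral-t power at the difference 2.04.
- Chance imbalance between two arms (1 SD) = k × 1.7 × √(2f(1 − f)/12).

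| f | k | Mean shift | Share of 3.9 | Between-arm power | Chance imbalance, 1 SD |
|---|---|---|---|---|---|
| 0.10 | 0.25 | 0.04 | 1% | 0.798 | 0.05 |
| 0.25 | 0.50 | 0.21 | 5% | 0.782 | 0.15 |
| 0.50 | 1.00 | 0.85 | 22% | 0.708 | 0.35 |

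**4. Within-arm pre/post test with no treatment effect.** In SD units, the SD of change is √(2(1 − r) + f(1 − f)k²), where r is the pre/post correlation (also assumed). The mean drift is f × k, and n = 12. The nominal false-positive rate is 0.05.

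| f | k | r = 0.5 | r = 0.8 |
|---|---|---|---|
| 0.10 | 0.5 | 0.053 | 0.057 |
| 0.25 | 0.5 | 0.067 | 0.091 |
| 0.50 | 1.0 | 0.29 | 0.50 |

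This takes all drift as one-directional. Opposing drifts, such as one drug wearing off in some subjects and another taking effect in others, would partly cancel in the mean and mainly widen the spread.

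**The case against.** The strongest reply is that the trial is randomised, double-blind and placebo-controlled. A reader might infer that recent drug changes bias the comparison of synbiotic or sevelamer with placebo. The documents do not support that: drift is balanced across arms in expectation, and what remains is noise and chance imbalance. Systematic bias there would need background doses to change in response to study treatment. This part of the reply stands.

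A reader might also infer from the current-practice section that recent switchers will be common. That section describes escalation when control is poor, not stopping. Subjects still on metformin or another non-permitted agent are already excluded as current users. No frequency is given, so this too stands.

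Nor do the documents say how long any antidiabetic drug affects the clamp, LPS or signalling. The 3-month period belongs to other agents, and nothing presents it as the right washout here.

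Two further replies stand in part. The gut-flora item is open-ended and could be read to cover a stopped antidiabetic that alters the microbiome; that would not deal with a changed sulfonylurea dose or with effects on the clamp. Colestyramine and systemic steroids do have a look-back, so the gap concerns antidiabetic drugs, not every glucose- or lipid-active drug. History-taking and eligibility review at entry could reveal a recent change, but no criterion acts on it.

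Finally, a stability condition would not remove all confounding at baseline, because stable sulfonylurea users would still occur only in the T2DM group.

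**Conclusion.** The gap is real, and nothing elsewhere in the documents closes it. It should be fixed, but it does not undermine the randomised contrast. There the cost is some precision: at 12 per arm, power falls from 0.80 to between 0.798 and 0.708, and the low end needs half the subjects affected by a full SD. The non-randomised T2DM analyses are more exposed. The baseline shift is 1% to 22% of the obese-T2DM difference, and the within-arm false-positive rate runs from barely above 0.05 to 0.29 (r = 0.5) or 0.50 (r = 0.8).

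These sizes rest on assumed values of f, k and r, on the assumed row label, on equal allocation and on one-directional drift. If few subjects are affected, the effect is minor.

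**What to change.** 1. **Eligibility text, Section 4.c, Population 3.** Reconcile the sulfonylurea exemption and the wording on current treatment with the stable-dose and look-back conditions already in the same list. This is an eligibility condition only: the sponsor sets the period, and nobody is taken off treatment for the study.
2. **Data collection.** Record antidiabetic drug history at entry and any dose change between Visits 4 and 6.
3. **Analysis, Section 6.a.** Pre-specify pre-baseline antidiabetic exposure as a covariate or sensitivity factor in the T2DM analyses. Report on-study dose changes by arm, descriptively. Keep all randomised subjects in the main contrast. Leaving out those whose dose changed would condition on a post-randomisation event, and Section 6.c allows that either intervention may improve glucose in T2DM, so such changes could depend on treatment.

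The cost is an eligibility amendment, one extra case-report field, a short addition to the analysis text and a somewhat smaller pool of eligible T2DM subjects.
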